9. QUALITATIVE STUDY

The qualitative component of this feasibility study aims to explore participants' experiences of the intervention programme and the study, and the individual and contextual factors that influenced their engagement. We will also explore how well the intervention supports people's weight management and emotional wellbeing and how the programme could be improved to provide better support.

The qualitative component will further explore the SWiM coaches' experiences of delivering the intervention programme, engaging with participants, and supporting participants with weight management and emotional wellbeing. We aim to explore how the programme could be improved in the future.

9.1 Data collection

Individual semi-structured interviews (n~30) will be conducted at the end of the study. Participants will be purposively sampled using outcome data (broad demographic, range of adherence and weight outcomes) in participants from both trial arms (2:1 ratio, intervention: control). Questions will focus on participants' experiences of SWiM, including the benefits and challenges experienced, their remaining needs at the programme end, and the extent and manner of programme implementation. Participants will receive a £20 gift voucher as an honorarium for taking part in the qualitative interview.

All SWiM coaches (n=7) will be invited to take in individual semi-structured interviews. Questions will focus on coaches' experiences of delivering SWiM-C, including the engaging with participants, supporting participants' needs, and the programme acceptability. Participants will receive a £20 gift voucher as an honorarium for taking part in the qualitative interview.

9.2 Analysis

Qualitative analysis will explore the perceived feasibility and acceptability of the programme; individual and contextual factors that influence implementation and effectiveness; what participants experienced as key facilitators or barriers to weight control during the pandemic; the impact the intervention had on emotional wellbeing, and any needs they felt were not met.

Data pertinent to different groups (intervention participants, control group participants, and SWiM-C coaches) will be analysed and presented separately. Findings will then be integrated narratively.

Recordings will be transcribed by an experienced external agency and checked for accuracy by the research team. Verbatim transcripts will be coded using NVivo software, retaining a focus on narrative sequences and transitions as well as salient themes. A dual coding approach will be used as follows: a first inductive round based on emerging themes relating to the research questions; a second round sensitised by quantitative findings. In the first inductive stage, open codes will be generated based on line-by-line scrutiny of verbatim transcripts uploaded into NVivo.

Inconsistencies between coders will be resolved through discussion.

10. DATA MANAGEMENT

10.1 Data Security

The MRC Epidemiology Unit has an over-arching data management policy (DMP) that encompasses the standards and processes applied to all research and operational activities in the Unit. The PIs will ensure that all data generated, stored and shared from this trial will be handled in compliance with the DMP and the General Data Protection Regulations. The data controller will be the University of Cambridge. The legal basis for holding and processing the data as outlined in the protocol is to enable the team to conduct health research in the public interest.

All electronic data will be held on the Unit's secure networks, collated in version controlled uniquely identified databases.

Participation will be under full informed e-consent, including for the storage and use of data collected. At any point, participants can choose to opt out of any aspect of data collection or processing. As stated on the information sheet, any data collected up until the point of withdrawal will continue to be held by the study team.

Personal identifiable data will be held in the Study Database developed by the MRC Epidemiology Unit Data Manager in SQL server. It will have secure encrypted transmission. This will only be accessed by the core study team at the University of Cambridge using designated usernames and passwords. The database will be kept on the unit's private network which is used for the storage of identifiable data. It is automatically backed up to ensure no loss of data. All systems are run by professional IT staff and data handling and back-up processes are managed to standards equivalent to those defined in the MRC Information Security Policy and meet the University of Cambridge Data Security Policy. The Study Coordinator and Data Manager will monitor the accuracy of the database

with validation checks against the data collection forms. All resulting datasets will be anonymised and stored securely. The study database will also be used to record study data, including randomisation group, eligibility criteria met and attendance at appointments. Questionnaire webforms will be held in separate link-anonymised data files, and will be linked to other data sources for analysis using a link file stored in the study database.

The SWiM web-platform has been developed by Cauldron Science Ltd and is stored securely on Microsoft Azure which is a secure cloud based web host. All data is stored in a Microsoft Azure SQL database; this is stored in two different data centres both located within the European Union. Data inputted into the SWiM web-platform, including name and email address are stored securely in the Azure SQL database, which is encrypted at rest and only accessible with both the correct credentials and a whitelisted IP address. The University of Cambridge and Cauldron Science Ltd hold a data confidentiality agreement. The web platform is stored in accordance with the University of Cambridge data standards and such data is only accessible to the study team and Cauldron as the technical providers. All content is the intellectual property of the University of Cambridge. The study team at MRC Epidemiology will be responsible for downloading the research data via a secure download directly from the SWiM platform.

The qualitative interviews will be carried out by phone or using zoom (chats will be password protected to ensure privacy) and will be recorded using an Epidemiology Unit Dictaphone. The recordings will be transferred to the Unit's secure network as soon as they have been recorded.

Recordings will be transcribed by an experienced external agency and checked for accuracy by the research team. Verbatim transcripts will be coded using NVivo software, retaining a focus on narrative sequences and transitions as well as salient themes. This will help us understand participants' accounts of what mattered for their weight control and how these aspects fit within the context of their everyday lives. A dual coding approach will be used: a first inductive round based on emerging themes relating to the research questions; a second round sensitised by quantitative findings. In the first inductive stage, open codes will be generated based on line-by-line scrutiny of verbatim transcripts uploaded into NVivo. Inconsistencies between coders will be resolved through discussion.

10.2 Link Anonymisation

Participants will complete an online screening questionnaire and will be assigned an anonymised participant ID number which will be unique to them. The Database Manager will have programmed a SWiM-C Protocol
ISRCTN12107048

series of ID numbers into the database which will be assigned to participants in sequence. The ID number and participant's personal details will need to be linked in a separate database to enable us to contact participants for further follow up visits, but access to this information will be restricted to the database manager and the study coordinator. At the point the participant has been assigned an ID number, this will be used thereafter on all Case Report Forms and questionnaires; the only form to include the participants name will be the consent form which will be kept separately to the other study documents. Link-anonymised ID numbers will also be used to access online questionnaires.

Participant details will only be used when we mail out study information (eg. Newsletters) and questionnaires.

10.3 Data Sharing during the Trial

Data sharing will be kept to the minimum required for the trial conduct and patient safety. Personal identifying information and outcome data will be kept separate at all times. Any data transfer will be encrypted and shared via a secure FTP server with appropriate data sharing agreements and consent in place.

Anonymised data sets may be shared with collaborators for research purposes. Each data request from outside the research team undergoes review by the PIs for scientific merit and integrity before any releases are made.

10.4 Data Forms and Data Entry

Online questionnaires will be completed via a dedicated programme that has been set up by the Data Team at the University of Cambridge. Online questionnaires will be exact copies of the paper forms. Data will be exported from the software programme by the study coordinator and saved on the secure network where 10% sense checks will be carried out. The Database Manager and the Study Coordinator will be responsible for data entry, quality and checking procedures.

10.5 Data Storage and Archiving

The Principal Investigators and Sponsor will take overall responsibility for data archiving with day to day responsibility delegated to the Database Manager and Study Coordinator. All data sets will be kept securely with no access from unauthorised personnel. Data will be stored so that it can be accessed, used and understood by subsequent users. When the investigators have completed their planned analyses, the anonymised data will be made available for use by others and will be shared under appropriate data sharing agreements. Primary data and the Trial Master File will be retained securely in their original form for a minimum of 10 years.

The MRC Epidemiology Unit will be responsible for archiving all documentation relating to the trial which will include consent forms, participant forms (screening questionnaires, CRFs, questionnaires), data, the study database, and results and associated files.

MRC policy is that: (i) primary research data are kept in original form for a minimum of 10 years from study end after which review will be carried out regularly to review retention; (ii) where consent has been taken, the original records covering the protocol, consent procedure, recruitment log and adverse event reports will be kept for 30 years after the end of the study in both digital and original form; and (iii) for clinical or public health studies, all records (other than those relating to consent) will be kept for 20 years to enable review and / or re-appraisal.

11. ADVERSE EVENTS

It is unlikely that we will experience adverse events as this is an online randomised controlled trial but in the event that we do, they will be reported according to unit policy and CETU SOP015 (Recording and reporting adverse events).

12. RESEARCH GOVERNANCE AND APPROVALS

The investigators will ensure that the trial conduct conforms to the principles of the Declaration of Helsinki (2008), ICH notes for Guidance on Good Clinical Practice and the Data Protection Act. All research participation will be done under written informed consent.

The protocol, participant information sheets, and e-consent form will be submitted for to the University of Cambridge Psychology Research Ethics Committee (PREC). No participants will be recruited until relevant approvals have been received. Where needed, the Investigators will submit any proposed substantial and non-substantial amendments to the protocol or other approved documents to the PREC for approval. Substantial amendments will not be implemented until relevant approvals have been given.

13. ROLES AND RESPONSIBILITIES

The MRC Epidemiology Unit, University of Cambridge is the lead institution. All Investigators contributed to the design of the protocol and the application for funding.

As Joint Principal Investigators, [name] and [name] have joint responsibility for the design and conduct of the trial and for the analysis and dissemination of results.

As the Study Coordinator, [name] will take responsibility for the day-to-day management of the trial at the MRC Epidemiology Unit. This will include day-to-day responsibility for: recruiting participants, monitoring recruitment and uptake, retention and online study completion; creating standard operating procedures; preparing reports for the sponsor, ethics committees and funders as appropriate; ensuring that the trial is running in a timely manner and in accordance with good clinical practice guidelines.

The Trial Statistician, [name], is responsible for overseeing the work of a dedicated Research Associate who will write and implement the statistical analysis plan.

[name] is responsible for leading the economic evaluation, including the establishment of the data collection methods used, conducting the quantitative analyses and publication and appropriate dissemination of findings.

[name] and [name] will lead the qualitative evaluation, including the establishment of the data collection methods used, conducting the qualitative analyses outlined in Section 9, and publication and appropriate dissemination of findings.

14. PATIENT AND PUBLIC INVOLVEMENT

The ideas for this study were developed in response to requests for support with eating behaviour and weight management from the European Patient Council on Obesity, who then reviewed the initial outline of the study and strongly supported its aims. Substantial PPI input was included in the development of the SWiM intervention. The initial ideas and research proposal were reviewed by 22 men and women attending the Fakenham Weight Management Service in Norfolk and 6 members of the University of Cambridge PPI Panel. Once funding was awarded a Patient User Group Panel (PUGP) was formed, comprising members with diverse experiences of weight loss and weight maintenance. This group helped in development and refinement of the logic model, the intervention outline, and different prototype iterations. Regular meetings were convened during the development phase, in order to consult on progress and to feedback to the panel on how their input was incorporated. A series of 'Think aloud' user testing sessions were completed for the alpha version of the web platform with feedback requested on content, design and functionality. To get feedback on the content from a wider and more diverse audience, remote user testing of the web platform has been conducted with the PUGP members and participants from the WRAP study from around the UK.

To maximise participant engagement and retention, and minimise burden, PPI representatives have also reviewed the content, design, and delivery of participant-facing materials. They will also advise on the content and methods of qualitative interviews and focus groups to ensure sensitivity and to maximise participant engagement.

A member of the PUGP will review the transcripts of the qualitative interviews, providing input to the analysis and interpretation of the findings. They will be included as a co-author on the qualitative results paper.

A PPI representative ([name]) is a member of our Investigator team and has contributed to the design of the protocol and chairs the PUGP. She will also contribute to designing and delivering PPI training, preparing ethics and R&D submissions, co-authoring journal articles and the final report, disseminating findings to a wide range of audiences, and supporting other PPI members.

Two PPI representatives are members of the Trial Steering Committee. They will review the final study reports and contribute to the writing of specific sections, such as the lay summary.

Including PPI perspectives in plans for dissemination will ensure that we access an appropriate range of audiences and communicate messages effectively. PPI representatives will advise on content and methods of dissemination and will review public facing documents such as newsletters and press releases.

PPI representatives will be reimbursed for their time and expenses in a timely manner and tailored PPI training will be provided to suit the specific needs of the individual and their role. We will use the INVOLVE Standards for PPI as a guide. All meetings will be virtual and tailored to individual needs as Covid-19 recommendations and regulations dictate.

15. PROGRAMME STEERING COMMITTEE

An independent trial steering committee will be established to ensure that the project is conducted to the rigorous standards set out in the UK Policy Framework for Health and Social Care Research and the Guidelines for Good Clinical Practice. The TSC will consist of at least 3 independent academics with relevant experience and 2 patient and public representatives. They will provide advice to the Investigators on all aspects of the trial and will review and agree the trial protocol, the statistical analysis plan, and any amendments to the protocol. This is a low risk trial with no rules for early stopping and participants and study coordinators are not blind to intervention allocation. Thus a separate data monitoring committee was not deemed to be necessary.

16. DISSEMINATION

At the end of the trial we will present our findings to our PPI representatives and our stakeholder panel and to identify appropriate ways to communicate findings to participants and other non-academic audiences. Co-authorship & co-presenting with our PUGP members will be sought where possible and the results will be made available to participations.

All specified analyses will be written up as scientific papers and submitted for publication in peer-reviewed open-access journals. Members of the research team will be involved in reviewing drafts of the manuscripts, abstracts, and any other publications arising from the trial. The Principal Investigators will have final approval on all publications and press releases. Authorship will be determined using ICMJE criteria.

In all papers or reports for publication the following statement (which incorporates a disclaimer in view of the independence of the research) should be used, amended accordingly, depending on the type of output:

“This paper/article/abstract presents independent research funded by the National Institute for Health Research (NIHR) under its Programme Grants for Applied Research Programme (Reference Number RP-PG-0216-20010) and the MRC Epidemiology Unit. The views expressed are those of the author(s) and not necessarily those of the NHS, the NIHR or the Department of Health.”

As a condition of NIHR funding, the Investigators must give 28 days’ notice of intention to NIHR prior to submitting a research paper and 14 days’ notice prior to the host institution or publisher or collaborator issuing a press release together with the draft manuscript.

### **SAP** revision history

Date	Version	Justification for SAP version
19/01/2022	1	First draft sent to [name]
20/01/2022	2	Comments from [name] incorporated, version sent round to wider team
15/03/2022	3	Comments from [name] incorporated
16/03/2022	3.1	Final edits from [name] and [name] incorporated, version signed off by [name] and [name]. Version sent to all co-authors.

# 1 Introduction

### 1.1 Trial background and rationale

The social distancing and isolation measures imposed during the COVID-19 pandemic beginning March 2020, including the closure or reduced operating of some weight management programmes and services, mean that adults with overweight and obesity in the UK are at increasing vulnerability to weight gain, and associated negative impacts on physical health and mental wellbeing. There is good evidence that interventions based on acceptance and commitment therapy (ACT) are effective for weight management and may improve mental wellbeing and psychological determinants of weight control.(4) However, acceptance-based programmes are usually psychologist-led and the cost and scarcity of psychologists specialising in obesity mean it is not possible to support everyone who would benefit from this type of intervention.

We developed a supported self-help intervention (SWiM-C; Supporting Weight Management during COVID 19) that aims to help adults with overweight and obesity to manage their weight and eating behaviour, be more physically active, and protect their emotional wellbeing during the COVID pandemic. The 12-week intervention is based on ACT, targets known psychological determinants of weight management and is delivered via an online platform with remote support from a guide or coach.

If the SWiM-C intervention proves to be effective it could be rolled out on a larger scale to support people in situations involving high levels of stress, reduced access to resources, and/or low levels of mobility.

We previously evaluated the effect of SWiM-C on bodyweight in adults with overweight and obesity at 4 months post intervention compared to standard advice (written materials giving advice on diet, physical activity and mental health during the COVID-19 pandemic). The data were compatible with no effect of the intervention on bodyweight, physical activity, mental health, or emotional eating. The intervention improved psychological determinants known to lead to successful weight management in the longer term (uncontrolled eating, cognitive restraint, and experiential avoidance) and had a protective effect on wellbeing.

The current study compares the effectiveness of SWiM-C with standard advice at 12 months post intervention.

### **1.2** Trial objectives/hypotheses

### Primary objective:

To evaluate the effect of SWiM-C on weight over 12 months compared to current standard advice for people with overweight and obesity.

### Secondary objectives:

- To evaluate the effect of SWiM-C over 12 months on eating behaviour, physical activity, health-related quality of life, capability and wellbeing, depression, anxiety, perceived stress, and experiential avoidance/psychological flexibility, compared to standard advice.
- To evaluate the effect of SWiM-C on change in weight from 4 months to 12 months, compared to standard advice

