5. PLANNED INTERVENTION AND CONTROL

5.1 Supporting Weight Management during the COVID-19 pandemic (SWiM) programme

SWiM is a supported self-help programme that uses acceptance-based strategies to support adults with overweight and obesity to manage their weight and eating behaviour, be more physically active, and protect their emotional wellbeing. The intervention includes access to an online web platform with 12 modules (SWiM sessions) consisting of psychoeducational content, reflective exercises, and behavioural experiments. Content is described in Table 1. SWiM is intended to be a 12 week intervention, with 1 session completed per week. Participants are encouraged to weigh themselves weekly and to record their weight at the start of each session. Between sessions, participants are asked to complete more reflective exercises and behavioural experiments known as 'SWiM Practice'. Automated email reminders are sent to participants to remind them to log in and complete sessions each week. After the participant has completed the week 4 session, they will receive a telephone call from their SWiM Coach. This will be a 20 minute call to check in and see how the participant is getting on with the intervention and to ensure they understand the content. A

tailored email will also be sent at week 10. At the end of the study, participants will then receive the same standard advice materials as the control group.

| Session | Content |
|--|---|
| Welcome to SWiM | What is SWiM? |
| | Let's take a tour around SWiM! |
| | Meet the SWiM Team |
| Session 1: Eating Well During Lockdown | 1.0 Tracking Your Progress |
| | 1.1 Eating Well During The Lockdown |
| | 1.2 Alcohol and COVID19 |
| | 1.3 SWiM Practice: Planning Your Meals |
| Session 2: Staying Active During Lockdown | 2.0 Checking in |
| | 2.1 Physical Activity and COVID19 |
| | 2.2 Physical Activity Recommendations |
| | 2.2 Tips for Staying Active |
| | 2.3 SWiM Practice: Your Physical Activity Plan |
| Session 3: Planning and Goal-Setting | 3.0 Checking in |
| | 3.1 Your Weight Maintenance Plan |
| | 3.2 SMART Goals and Plans |
| | 3.3 SWiM Practice: Goal Setting |
| Session 4: Control and Acceptance | 4.0 Checking in |
| | 4.1 Control and Acceptance |
| | 4.2 What Matters to You? |
| | 4.3 SWiM Practice: Values, Goals and Actions |
| Session 5: Being Willing | 5.0 Checking in |
| | 5.1 Values and Goals |
| | 5.2 Being Willing |
| | 5.3 SWiM Practice: 'Even If...' Thoughts |

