5.2 Control Intervention

Participants who are randomised to the control arm will receive standard advice from the European Association for the Study of Obesity (EASO) on diet, physical activity and mood during the COVID 19 pandemic.(6) They will also be wait-listed to receive access to the SWiM website after the study ends.

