7.2 Outcome Assessments

All outcomes will be assessed via online self-report questionnaires. Participants will be asked to weigh themselves on the day that they complete the outcome assessment so that they can report a self-measured weight. At 12 months, intervention and control participants will complete the intervention engagement questionnaire, since control participants received access to the SWiM website after the 4-month follow-up. This will allow us to control for intervention engagement in analyses, and to compare intervention experiences between intervention participants who received the website in conjunction with support by a coach, and control participants who received only the website without coach support.

Participants will complete a demographics questionnaire at baseline based on Progress-Plus(16) factors.

The study coordination team will send email/phone reminders to participants if a questionnaire has not been completed after 7 days.

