8. STATISTICS AND QUANTITATIVE DATA ANALYSIS

8.1 Statistical analysis

A detailed statistical analysis plan will be developed and signed off by the Trial Steering Committee (TSC) prior to analysis. Participants will be analysed in the group to which they were randomised, based on the intention-to-treat principle. The primary analysis will estimate the baseline-adjusted difference between intervention groups in change in weight from baseline to 4 months, using a linear regression model including randomisation group, baseline weight, and the randomisation stratifiers (sex, BMI classification). Participants with missing values of weight at 4 months will be excluded (ie, a complete-case analysis which assumes outcome data are missing at random conditional on covariates in the model). If there are >5% of participants with missing values of weight, a sensitivity analysis will be performed using multiple imputation by chained equations – this makes the missing at random assumption but provides increased precision compared with a complete-case analysis. Linear regression will be used to estimate the baseline-adjusted difference between intervention groups in change in weight from baseline to 12 months and 4 months to 12 months. Since the control group was waitlisted and therefore received access to the SWiM website after the 4-month follow-up, analyses at 12 months will need to account for intervention usage in the control group. Regression models for the 12-month follow-up will therefore include intervention engagement (as measured using the intervention engagement questionnaire and/or website analytics) as a covariate. Full details of this analysis will be provided in the statistical analysis plan. Continuous secondary outcomes will be analysed using the same method.

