### 2.2 Control

The wait-list control group received standard advice in the form of a leaflet from the European Association for the Study of Obesity (EASO) on diet, physical activity, and mood during the COVID 19 pandemic, tailored to people living with obesity. After completing 4-month follow-up assessments, participants in the standard advice group were provided access to SWiM-C.

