### Secondary outcomes

Continuous secondary outcomes will be analysed using the same approach as described for the primary outcome.

We will estimate baseline-adjusted differences between the study groups in change in weight from 4 months to 12 months using a linear regression model with change in weight from 4 months to 12 months as the outcome, and including baseline weight, 4 month weight, the randomisation stratifiers (sex, BMI classification) and intervention group as covariates.

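### The 4-to-12-month weight objective names standard advice as the comparator, but controls had SWiM access in that window, so the planned coefficient cannot answer it

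*SAP*

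**What the plan says.** The second bullet under Secondary objectives in SAP 1.2 reads "To evaluate the effect of SWiM-C on change in weight from 4 months to 12 months, compared to standard advice". SAP 5.2 (Secondary outcomes) supplies the analysis: "We will estimate baseline-adjusted differences between the study groups in change in weight from 4 months to 12 months using a linear regression model". The covariates are group, baseline weight, 4-month weight and the stratifiers. Protocol 8.1 lists the same contrast, "change in weight from baseline to 12 months and 4 months to 12 months", as a difference between the randomised groups.

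On what each arm receives:

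- Intervention arm, Protocol 5.1: "SWiM is intended to be a 12 week intervention, with 1 session completed per week".
- Control arm, SAP 2.2: "After completing 4-month follow-up assessments, participants in the standard advice group were provided access to SWiM-C".
- Protocol 7.2 describes what controls had: "control participants who received only the website without coach support".
- Protocol 8.1 draws a consequence: "analyses at 12 months will need to account for intervention usage in the control group". It plans an engagement covariate in the 12-month models.
- Protocol 5.2 says something different about timing: "They will also be wait-listed to receive access to the SWiM website after the study ends".

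**The concern.** The objective promises a comparison with standard advice over months 4 to 12. On the account in SAP 2.2, Protocol 7.2 and Protocol 8.1, that comparator no longer exists in this window: controls can start SWiM, while the arm labelled SWiM is past its scheduled programme.

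This differs from the baseline-to-12-month contrast. That contrast still contains the first four months, when SWiM was compared with standard advice, so later control access contaminates only part of it. The 4-to-12-month window leaves those months out and keeps only the period after controls gained access.

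The stake is how the result is read. Under the SAP 1.2 label, a coefficient favouring controls would be reported as SWiM doing worse than standard advice, and a coefficient near zero as no effect against standard advice. The data in this window test neither statement.

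**Working it through.** **1. Who has what between months 4 and 12.** Four months is 4 × 52/12 = 17.3 weeks, so a 12-week programme begun soon after randomisation is due to end about 5 weeks before the assessment. Controls gain access after it. If they kept the same weekly pace (an assumption), their programme would last 12 ÷ (52/12) = 2.8 months and end near month 7, inside the window.

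**2. Whether the SAP handles this elsewhere.** The 4-to-12-month model has no engagement term, although Protocol 8.1 plans one for the 12-month models. SAP 5.5 explains the move to a random intercepts model but not the loss of that term. The per-protocol analyses in SAP 5.2 repeat only the primary outcome analysis. SAP 3.2 counts control access at 1, 4, 8 and 12 sessions and goes no further. Engagement is measured after randomisation, so adding it as a covariate would not restore a standard-advice comparison.

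**3. The plan's own figure.** Protocol 8.2 gives a 1 kg difference, SD 6 kg, correlation 0.9, 90% power, 5% level and 20% dropout. Taking the test as two-sided:

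- residual SD = 6 × √(1 − 0.9²) = 2.615 kg
- n per arm = 2 × (1.960 + 1.282)² × 2.615² / 1² = 143.8, so 144
- 144 / 0.8 = 180 per arm, 360 in total

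This matches the protocol. It covers the 4-month comparison; no design figure is given for months 4 to 12.

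**4. What the SAP's coefficient estimates.** Write differences as intervention minus control, so positive is against SWiM. Let τ4 and τ12 be the differences in mean weight at 4 and 12 months. Assume:

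- τ4 = −1 kg (the design difference)
- r = fraction of that effect regained by the intervention arm by month 12
- c = share of that effect gained by controls after access (uptake times relative effect)

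The documents give neither r nor c. Then τ12 = −(1 − r) + c.

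- Simple difference in change: τ12 − τ4 = r + c.
- SAP model, which adjusts for 4-month weight: τ12 − b·τ4 = −(1 − r) + c + b, where b is the slope of 12-month on 4-month weight given baseline weight.

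The protocol gives one correlation, 0.9, and no pattern, so two are shown:

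- all pairs 0.9: b = 0.9 / (1 + 0.9) = 0.474
- decaying, 0.9 between neighbouring visits and 0.81 from baseline to month 12: b = (0.9 − 0.9 × 0.81) / (1 − 0.81) = 0.171 / 0.19 = 0.90

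The stratifiers are left out for simplicity.

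| r | c | Simple difference (kg) | SAP model, b = 0.474 | SAP model, b = 0.90 |
|---|---|---|---|---|
| 0 | 0 | 0.00 | −0.53 | −0.10 |
| 0 | 0.25 | +0.25 | −0.28 | +0.15 |
| 0 | 0.5 | +0.50 | −0.03 | +0.40 |
| 0 | 1 | +1.00 | +0.47 | +0.90 |
| 0.5 | 0.5 | +1.00 | +0.47 | +0.90 |
| 1 | 1 | +2.00 | +1.47 | +1.90 |

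Simulating the same regression with 400,000 participants agreed to within about 0.03 kg at the settings checked.

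**5. Reading the table.** In every column, a rise in c moves the result by the same amount against SWiM. The sign is another matter. With full maintenance (r = 0) the SAP model crosses zero at c = 1 − b, that is 0.53 or 0.10. With r = 0.5 it crosses at 0.5 − 0.474 = 0.03 under equal correlations, and is already +0.40 kg at c = 0 under decaying ones. The rows r = 0.5, c = 0.5 and r = 0, c = 1 give identical values: the coefficient depends only on r + c and cannot separate regain from control benefit.

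**The case against.** The strongest case for leaving the plan alone has five parts.

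- **The wait-list is disclosed.** Protocol 8.1 and SAP 5.2 describe this contrast only as a difference between groups. That is right, and it confines the wording fault to the SAP 1.2 bullet. The fault remains there, because an objective says what a result will be taken to mean.
- **The outcome is exploratory.** SAP 3.1 treats it so and reports no p-value. This limits the harm but does not supply the missing comparator.
- **The effect on the estimate may be small.** SAP 1.1 reports no clear weight effect at 4 months, controls had no coach, and their uptake is unknown. This stands as a limit on size. A near-zero estimate would still be reported against a comparator that was not there.
- **A later benefit is plausible.** SAP 1.1 reports improved psychological determinants linked to longer-term weight management, so the intervention arm might gain further, moving the coefficient in SWiM's favour. This stands, and is one reason why no direction can be fixed.
- **Twelve weeks is an intended schedule.** The platform is designed for revisiting past sessions, and nothing says the intervention arm lost access. This also stands: it softens any claim that the arm had stopped using SWiM, but does not return controls to standard advice.

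A reader might infer more: that the arms are simply reversed, and that an effective programme must show a difference of r + c kg against SWiM, negative only if the intervention arm improves further after its programme. The documents do not support that. The formula r + c belongs to the simple difference in change; the SAP adjusts for 4-month weight, and at r = 0, c = 0.25 its model gives −0.28 or +0.15 kg. Nor do they support declaring in advance that a difference favouring controls is expected and is no sign of inferiority. That would explain away real regain, which this contrast cannot tell from control benefit.

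**Conclusion.** The objective is wrong as written. The planned coefficient cannot estimate the effect of SWiM-C against standard advice between months 4 and 12, because controls had website access to SWiM-C in that window. It compares follow-up after earlier coach-supported SWiM with follow-up after delayed website-only access, and no other planned analysis repairs this.

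Each unit of benefit controls gain moves the coefficient by one unit against SWiM, but the final sign is undetermined. The break-even control gains of about 0.10 and 0.53 kg rest on an assumed, fully maintained 1 kg effect at 4 months and on the two assumed correlation patterns. Under the same share-of-effect assumptions, a smaller 4-month effect shrinks all the figures in proportion.

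The structural conclusion needs none of these values. It needs only that controls had access from month 4, as SAP 2.2, Protocol 7.2 and Protocol 8.1 state and Protocol 5.2 contradicts. One exploratory secondary objective is affected. This point does not bear on the 4-month comparison or the sample size.

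**What to change.** 1. In SAP 1.2, restate the objective as the difference in 4-to-12-month weight change between earlier coach-supported SWiM and delayed website-only access. Do not report it as an effect against standard advice. The group wording in SAP 5.2 and Protocol 8.1 can stay.
2. Add 95% confidence intervals to the within-arm 4-to-12-month changes, for which SAP 5.2 (Primary outcome) already plans means and SDs. Present them as descriptive.
3. State in advance, neutrally, that the contrast cannot separate regain in the intervention arm from benefit in controls. Neither a difference favouring controls nor a null result is then, by itself, evidence for or against SWiM relative to standard advice.
4. Reconcile Protocol 5.2 on the timing of control access with Protocol 7.2, Protocol 8.1 and SAP 2.2.

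The cost is a few sentences and two intervals from data the plan already collects. The downside is that one exploratory secondary objective can no longer be reported as an effect against standard advice.
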